Participants. 120 older individuals using the aforementioned applications at the Brookline Senior Living communities, the largest owner and operator of senior living communities across the United States (1000+ communities, 100,000+ residents) where the average age of residents are 85 years old. With respect to study interest across each community, we have reached out to the resident directors at each non-demented community to gauge interest in this program: 84% of the resident directors believed at least some of their constituents would be interested in participating, with 73% of these respondents estimating between 1-10 individuals per site. Given that this is a feasibility study assessing: i) working with this seldomly studied population, ii) the implementation of mobile technology in a senior living community, and iii) the utility of a cognitive assessment that prescribes a personalized intervention regimen, an initial foray into this population with such an approach is well positioned for this particular R21 mechanism.

Markers of success. The primary aim of this pilot study is to gather information about the feasibility of utilizing this type of assessment/intervention combination in a senior living community to set up a future R01 application. To that end, our markers to assess feasibility will include: 1) how participating individuals and resident directors accept participating in this project, as assessed through exit surveys with each group, 2) how many eligible participants enrolled/participated/dropped out of this study, 3) what was the quality of the collected data (was there excessive missing/unusable data?), and 4) limited-efficacy testing to examine the expected degree of responsiveness to the two versions of the intervention.

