Sample size. A power analysis to determine the needed sample size for this study resulted in us having to recruit a minimum of N=120 (40 in each condition) to achieve a balanced factorial design, which should be quite attainable given the interest indicated by the resident directors. Assuming 25% attrition, our recruitment plan will yield 90 participants, which will allow us to assess changes in performance as a function of training. Given the number of primary comparisons (3 scores of cognitive control at 2 time points (Pre- and Post-training)), there would be 95% power to reveal a group X session interaction on any given outcome, even with only 90 total participants split across the 3 groups. This corresponds to a medium effect size of .53, which is reasonable for a feasibility study of this size given the study-associated logistics. Pre- and post-training outcome data will be modeled using mixed within- and between-subjects GLMs and multivariate regressions¹⁰⁹. Significant interactions will be interrogated with appropriate follow-up tests between each group, including the direct assessment of effect size comparisons calculated using Satterthwaite's approximation¹¹⁰.

[figure not shown]
The goal of this R21 is to test the feasibility of deploying a targeted digital health remediation program for older adults in senior living communities based upon an initial characterization of these abilities. Below we discuss the logistics towards realizing this goal.

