Mixed Model Approach. Here we propose to use a sequential exploratory mixed method design¹¹⁵⁻¹¹⁹ for this pilot study. Specifically, a quantitative design will be used to: (1) collect descriptive information regarding older adults' perceptions of each app to enhance the UX experience for this particular population to explore the feasibility of self-administration for cognitive assessment and remediation, and (2) make pre-, post-, within- and across-group comparisons of cognitive functioning based on neurocognitive test performance and self-rated assessments. The qualitative approach will begin with local semi-structured interviews regarding the use of each app, first in a group of 10 one-on-one sessions with seniors led by our UX testing consultant (see **Letter of Support**), followed by subsequent interrogation by senior-centric UX group testing group (Longevity Explorers™, see **Letter of Support**) whose members are seniors trained in UX design refinement. Using data gathered from these experiences, we will augment the UX design of each app for subsequent dissemination to the Brookdale Senior Centers for use. Brookdale participants will be asked questions about their experience following training, with feasibility of program participation assessed quantitatively by measuring the number and percentage of sessions completed per participant. Questions at this time point (previously used by Hill and colleagues⁹⁰) will include "Do you feel your everyday thinking abilities have changed from doing the computer exercises and, if so, how? 2. What did you like about doing the computer exercises? 3. What did you dislike about doing the computer exercises? 4. Now that the study is over, would you keep doing the computer exercises?" Responses during said interviews will be transcribed, with frequency tallies of response consistencies per question across participants being tabulated. We will perform thematic analyses for the identification of important patterns/themes⁹⁰, creating a coding framework that maximizes coherence amongst categories emerging from the qualitative data¹²⁰⁻¹²².

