Assessments. All OAs will complete assessments at two periods: baseline and immediately following the intervention. In addition to measuring transfer to benefits to cognitive control (using ACE), we will also assess transfer of gains to functionally-relevant outcome measures, notably the Everyday Cognition Scale (ECog) to assess their ability to perform everyday tasks that demand memory, language, visuospatial abilities, planning, organization, and divided attention^{125,126}. The ECog scale has been used in other cognitive interventions trials and proven to be sensitive enough to detect improvements in healthy OAs and differentiate OAs from mild MCI^{127,128}. This survey will be sent directly to participants via an automated email campaign from Qualtrics™, with help from local resident mentors to complete these surveys on the same devices. Other surveys sent through this mechanism will include: i) a customized survey assessing participant expectancy across groups to further explore possible uncontrolled placebo effects (see for a description of this approach), ii) distractibility (via the Cognitive Failures Questionnaire)¹²⁹, and general health and well-being (SF-36)¹³⁰.

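### Participants who stop early have no stated route into the acceptability marker, so it may rest on about 90 of 120 and is probably, though not certainly, biased upward

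*Combined protocol and SAP*

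**What the plan says.** All references are to the combined protocol and SAP.

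- **Markers of success** makes feasibility the primary aim. Its first marker is "how participating individuals and resident directors accept participating in this project, as assessed through exit surveys with each group". The two groups in that sentence are participants and resident directors. Its second marker is "how many eligible participants enrolled/participated/dropped out of this study".
- **Mixed Model Approach** gives the only participant experience questions: "Brookdale participants will be asked questions about their experience following training". The fourth reads "Now that the study is over, would you keep doing the computer exercises". Answers are given in interviews, transcribed, tallied by frequency and analysed by theme. The same section assesses participation by "measuring the number and percentage of sessions completed per participant".
- **Assessments** sets the data-collection points: "All OAs will complete assessments at two periods: baseline and immediately following the intervention".
- **Sample size** plans to "recruit a minimum of N=120 (40 in each condition" and then states: "Assuming 25% attrition, our recruitment plan will yield 90 participants".
- **Protocol** and **Infrastructure Support** describe weekly feedback, real-time adherence tracking through a web portal, telephone and email support, and onsite help from resident directors.

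No section says whether someone who stops early is surveyed or interviewed, whether the reason for stopping is recorded, or how non-response enters the acceptability result.

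**The concern.** Someone who stops in week 2 of a 6-week programme is not naturally reached by questions put after training, and the fourth question does not fit that person's situation. If the plan is followed as written, the people most likely to have found the programme burdensome or unhelpful could be missing from the measure meant to detect it.

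Two things are at stake. The acceptability result taken into the future R01 application could be too favourable. The reasons for leaving, which would show what to change, could also be lost, and they are hard to recover if not collected at the time. The dropout count and the sessions completed show that people left and how much they did. They do not show why they left or what they thought.

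**Working it through.** **Inputs from the plan.** Planned enrolment is 120 (40 per arm) and attrition is 25%, both from Sample size. I treat all 120 as randomised.

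**Inputs the plan does not give.** There is no acceptability rate for completers or dropouts. I assume 80% in completers, varied from 60% to 90%, and let dropouts range from 0% to 100%.

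**Step 1: the plan's own figure.** 120 × (1 − 0.25) = 90, as stated. The remaining 30 (10 per arm if losses are equal) are those who could be absent from the acceptability data.

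**Step 2: bias formula.** Let p_c be the rate in completers and p_d the rate in dropouts.

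- All-randomised rate = 0.75 × p_c + 0.25 × p_d
- Bias of the completers-only rate = p_c − (0.75 × p_c + 0.25 × p_d) = 0.25 × (p_c − p_d)

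**Step 3: p_c = 80%, that is 72 of 90.**

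| Dropouts who find it acceptable | All-randomised rate | Error of the completers-only 80% |
|---|---|---|
| 0% (0 of 30) | 72/120 = 60% | +20 points |
| 10% (3 of 30) | 75/120 = 62.5% | +17.5 points |
| 50% (15 of 30) | 87/120 = 72.5% | +7.5 points |
| 60% (18 of 30) | 90/120 = 75% | +5 points |
| 80% (24 of 30) | 96/120 = 80% | 0 |
| 100% (30 of 30) | 102/120 = 85% | −5 points |

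**Step 4: other completer rates.** With p_d = 0 the largest overstatement is 0.25 × 60 = 15 points at p_c = 60%, and 0.25 × 90 = 22.5 points at p_c = 90%.

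**Step 5: other attrition rates.** With 80% in completers and 40% in dropouts (both assumed), the bias is 0.10 × 40 = 4 points at 10% attrition, 10 points at 25%, and 16 points at 40%.

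**Step 6: would the confidence interval reveal it?** The Wilson 95% interval for 72/90 is 70.6% to 87.0%. The all-randomised rate falls below it when p_d is under (0.706 − 0.60)/0.25 = 0.42. That interval reflects sampling error among completers only and was never an interval for all randomised participants.

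**Step 7: effect of reaching some early leavers.** If a fraction s of dropouts answers, the observed rate is (0.75 × p_c + 0.25 × s × p_d)/(0.75 + 0.25 × s). With p_c = 80%, p_d = 40% and s = 0.5, this is 0.65/0.875 = 74.3% against a true 70%. The bias falls from 10 points to about 4. With s = 1 it is zero.

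**The case against.** The strongest reply is that the plan is silent on early leavers rather than excluding them.

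- An exit survey of participating individuals can be given to anyone who exits, early or late. The plan also cites a Recruitment and Retention Plan that is not in the text available, and withdrawal procedures could be there. This stands. A reader might infer that dropouts are not surveyed; the documents do not support that as fact.
- The questions in Mixed Model Approach are interview questions, introduced as a list that need not be complete, and are not expressly equated with the exit survey. This also stands, and it weakens the fourth question as evidence of who receives that survey. They remain the only participant experience questions described.
- A reader might infer that acceptability is overstated, by 5 to 17.5 points. That range comes from assuming 10% to 60% acceptance in dropouts against 80% in completers, so it can only show overstatement. The average resident age is given as 85, and some people may leave for reasons unrelated to the programme. If dropouts think as completers do, there is no bias.
- The 25% is attrition for the performance data, not survey non-response. Someone who stops training could still answer, so 30 missing is an assumption about the survey.
- Dropout counts, data quality, session completion and resident-director surveys are reported too, so a reader could bound the acceptability figure. This stands in part: none of these supplies participants' reasons or opinions.
- The plan sets no acceptability threshold for proceeding, so no stated decision turns on the figure. That limits the consequence but does not remove the gap in a marker of the primary aim.

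**Conclusion.** The concern holds as a gap with a probable direction. As written, the plan gives early leavers no stated route into the first feasibility marker, and acceptability may rest on about 90 of 120 participants. The bias would be 0.25 times the difference between completer and dropout rates. With an assumed 80% in completers and nothing known about dropouts, the all-randomised rate could be anywhere from 60% to 85%, a 25-point range that a completers-only figure would not show.

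Upward bias is the likelier direction, because people who dislike a programme are more apt to leave it, but that is a judgement and not a result in the documents. The size rests on the assumed acceptability rates and on taking the plan's 25% as survey loss. The point does not invalidate the trial. It deserves action because it touches the primary aim and is cheap to settle before launch.

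**What to change.** 1. State that the exit survey or interview is offered at the earlier of the end of training or the decision to stop. The existing adherence tracking can flag people who have stopped. Email, telephone or onsite support can then be used to reach them.
2. Reword the fourth question for early leavers and record the reason for stopping.
3. State whether the Mixed Model Approach interview questions are the exit survey named under Markers of success.
4. Report acceptability by arm with all randomised participants as the denominator, beside the completers-only figure. Add best-case and worst-case bounds, counting non-responders first as all accepting and then as all not accepting. With 24 of 30 completers accepting in an arm of 40 and no early leaver answering, the bounds would be 24/40 = 60% and 34/40 = 85%.

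The cost is a small number of extra contacts, some by telephone because the described questions are interviews, and a few more table rows. Response from early leavers will be incomplete, so the bounds will narrow but may not close. The headline figure may be less favourable.

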Protocol. Following the initial local UX testing, a convenience sample of 120 older adults will be recruited from throughout the Brookdale Senior Centers throughout the United States (see **Figure 3**; see **Recruitment and Retention Plan** for additional participant enrollment details). These individuals will be asked to complete the battery of tasks on the ACE platform (~45min) to characterize cognitive control abilities before and after the assigned intervention. Following their initial assessment, each participant will be randomly assigned (using a pseudo-randomized blocked design using blocks of 9 to ensure equivalent representation across groups) to a one of three intervention types: directed training (DT) on the ACCT platform, non-directed training (nDT) on the ACCT platform, or an expectancy-matched placebo control platform (PC). We will ask each resident director and their residents to refrain from discussing their assigned intervention with other communities to preserve blinding across sites. The total training experience will encompass 6 weeks of training (3 days/week), with each training session lasting 36 minutes (not including self-paced breaks). Each participant in the DT and nDT groups will engage in 12 3-minute blocks of submodules in each training session on the ACCT platform. However, those in the nDT group will play each of the three submodules 4 times equally, while participants in the DT group will play 12 blocks proportionally weighted towards the cognitive control domain(s) that are most deficient at baseline as determined by their baseline ACE performance, and thus most likely to benefit from directed training. For example, if (following the ACE assessment) a given individual shows deficiencies on their attention and working memory scores but normal performance in their goal-management abilities, they will be prescribed 5 training runs of the attention & working memory modules and only 2 of the goal management module. Customization of each DT participant regime will be accomplished via a web portal at UCSF that transmits personalized training parameters directly to the individual's ACCT application. Each training program contains self-guided instructional videos and practice modules for each treatment, consisting of 6 weeks of training (3 days per week). Training sessions are linked, such that the next session begins at the level attained at the end of the previous session. Participants are provided two types of feedback: 1) real-time feedback – indicating whether the participant successfully detected or classified the target and 2) punctuated feedback – participants advance through a series of “levels” that are reported at the beginning and end of each run. We will provide weekly feedback about intervention use and performance improvement (in addition to daily in-app feedback), in support of its utility found in a recent survey¹²³: 79% of health app users indicated that periodic feedback about their app usage encouraged them to continue.

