
```

graph TD
    A["Pseudo-randomize individuals participants (9 per block design)"] --> B["DT"]
    A --> C["nDT"]
    A --> D["PC"]
    B --> E["ACE & Surveys  
Baseline"]
    C --> E
    D --> E
    E --> F["6 week of training"]
    F --> G["ACE & Surveys  
Follow-up"]
    G --> H["ACE & Surveys"]
    style A fill:#e0e0e0,stroke:#000,stroke-width:1px
    style B fill:#fff,stroke:#000,stroke-width:1px
    style C fill:#fff,stroke:#000,stroke-width:1px
    style D fill:#fff,stroke:#000,stroke-width:1px
    style E fill:#fff,stroke:#000,stroke-width:1px
    style F fill:#fff,stroke:#000,stroke-width:1px
    style G fill:#fff,stroke:#000,stroke-width:1px
    style H fill:#fff,stroke:#000,stroke-width:1px
    
```

Expectancy-Matched Placebo Control. The placebo control group (PC) will engage in a battery of three apps delivered in the same prescribed manner as the other two groups, which we hypothesize as based on our experience will have minimal positive impact on the cognitive abilities we are assessing: i) an app with 100 different logic games of varying difficulty and length, ii) a language-learning app with 10 language options, and iii) an app that offers a guided Tai Chi program. The total training experience here will also be for 6 weeks (3 days/week), with each training session lasting ~30 minutes where participants will be asked to use each of the submodules for 10 minutes (not including self-paced breaks). We have already determined that this approach generates matched expectancy of benefits compared to our training groups by questioning 100 naïve individuals to predict their expected improvement on each cognitive domain after training on these apps (see ¹²⁴ for details of expectancy testing). This revealed that placebo training generates equivalent expectations of improvement across each outcome measure as the DT group, thus serving as an effective placebo condition. Furthermore, initial pilot work examining transfer effects following training on this battery has shown no evidence of improved cognitive control with respect to attention or working memory abilities, supporting its utility as a placebo control.

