Infrastructure Support. Brookdale has already established an elegant infrastructure for sending, tracking, and gathering information as needed across all of their communities. Brookdale has 100,000+ residents in 47 states, divided into 5 geographic divisions, with several communications channels that provide resources on a monthly basis for Resident Programs associates. Each geographic division is led by a Directors of Resident Programs Engagement who supports the Resident Programs Associates in approximately 200+ communities. Each division is divided into approximately 50 areas, with each area supported by a Resident Programs “mentor”, and this team of 50+ mentors directly interacts with 15-20 communities. Resident directors have agreed to assist community residents in downloading and providing in-person help for this study, with [name] running a distributed webinar for all resident directors to teach them about these tools prior to study launch. Telephone and email support by the study team will be provided throughout the training period, in addition to active onsite support via resident directors. Each app will be configured to wirelessly transmit data automatically to our secure HIPPA-compliant server at UCSF when each training session is completed, with a custom web-portal facilitating data tracking in real-time to monitor participant adherence and data quality.

Markers of success. The primary aim of this pilot study is to gather information about the feasibility of utilizing this type of assessment/intervention combination in a senior living community to set up a future R01 application. To that end, our markers to assess feasibility will include: 1) how participating individuals and resident directors accept participating in this project, as assessed through exit surveys with each group, 2) how many eligible participants enrolled/participated/dropped out of this study, 3) what was the quality of the collected data (was there excessive missing/unusable data?), and 4) limited-efficacy testing to examine the expected degree of responsiveness to the two versions of the intervention.

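### The non-disclosure request covers other communities, but individuals are randomized, so co-residents in different arms are left out

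*Combined protocol and SAP*

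**What the plan says.** The Protocol section states that "each participant will be randomly assigned (using a pseudo-randomized blocked design using blocks of 9 to ensure equivalent representation across groups") to directed training (DT), non-directed training (nDT) or the placebo control (PC). The flow chart says the same: "Pseudo-randomize individuals participants (9 per block design"). Nothing in the supplied text assigns whole communities to an arm or stratifies by community.

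Recruitment is described as follows: "a convenience sample of 120 older adults will be recruited from throughout the Brookdale Senior Centers throughout the United States". For further enrollment details the section points to the "Recruitment and Retention Plan", which is not in the supplied text.

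The one request about disclosure is in the Protocol section. Resident directors and their residents will be asked to "refrain from discussing their assigned intervention with other communities to preserve blinding across sites".

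Two other sections bear on the point:

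- **Infrastructure Support:** "Resident directors have agreed to assist community residents in downloading and providing in-person help for this study". The study team also plans on "running a distributed webinar for all resident directors to teach them about these tools prior to study launch".
- **Expectancy-Matched Placebo Control:** the choice of comparator is justified by a test in 100 naïve individuals. "This revealed that placebo training generates equivalent expectations of improvement across each outcome measure as the DT group".

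**The concern.** The request and the randomization work at different levels. With individual allocation, two residents of the same community may be in different arms, and the request as worded does not ask them to keep their programs to themselves. It covers contact between communities, where contact is likely to be least frequent.

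The contrast at issue is the ACCT platform (DT or nDT) against the placebo apps: logic games, language learning and Tai Chi. These differ visibly. At a community with both, the resident director would help install and support both.

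The placebo comparison relies on the groups having matched expectations. That matching was tested in people who were not watching a neighbour use a different program for six weeks. If participants compare programs, expectations could diverge. The measures most exposed are the self-reports (Everyday Cognition Scale, Cognitive Failures Questionnaire, SF-36) and the post-training questions in the Mixed Model Approach section. The performance-based ACE scores behind the power statement are less exposed.

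**Working it through.** The plan gives no figure on this point, so there is none to reproduce. The check compares the text and then asks how often the gap could arise.

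**Text.** The unit of allocation is the individual, both in the Protocol section and in the flow chart. The request extends only to other communities. No other section asks participants in the same community to refrain from discussing their programs. The expectancy survey under Assessments measures expectations but does not restrict disclosure.

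**Inputs.**

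- 120 participants, 40 per condition (Sample size), hence 80 on ACCT and 40 on placebo.
- Participants per site, *m*: not fixed in the documents. Under Participants, 73% of the responding directors estimated 1 to 10 individuals per site. That is interest, not enrollment, so *m* is an assumption.
- More than 1000 communities (Participants).

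**Even spread, independent 1:1:1 assignment.** A site is mixed unless all its participants are on ACCT (probability 2/3 each) or all are on placebo (1/3 each):

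P(mixed) = 1 − (2/3)^m − (1/3)^m

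| m | Sites (120/m) | P(mixed) | Expected participants at a mixed site (120 × P) |
|---|---|---|---|
| 1 | 120 | 0 | 0 |
| 2 | 60 | 1 − 4/9 − 1/9 = 4/9 = 44% | 53 |
| 3 | 40 | 1 − 8/27 − 1/27 = 18/27 = 67% | 80 |
| 5 | 24 | 1 − 32/243 − 1/243 = 210/243 = 86% | 104 |

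**Effect of blocking.** If all *m* participants of a site fall in the same block of 9 (six ACCT, three placebo), then P(mixed) = 1 − [C(6,m) + C(3,m)] / C(9,m):

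- m = 2: 1 − (15 + 3)/36 = 50%
- m = 3: 1 − (20 + 1)/84 = 75%
- m = 5: 1 − (6 + 0)/126 = 95%

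Independent assignment therefore gives somewhat lower figures than this case.

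**Sparse scatter.** Suppose instead that the 120 participants fall at random over 1000 communities. Each of the 80 ACCT users has 40 placebo users who might share the site, and each of the 40 placebo users has 80 ACCT users:

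80 × (1 − 0.999^40) + 40 × (1 − 0.999^80) = 3.1 + 3.1 = 6.2 participants

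The number exposed thus runs from none or a handful to most of the sample, depending on how recruitment clusters.

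**The case against.** The strongest reply is that the sentence is addressed to directors as well as residents. A director has no individual allocation, so the wording about blinding between sites reads naturally as one intervention per community. If that were the design, there would be no mixed communities and this concern would fall away, although the analysis would then raise a different question. This reading cannot be excluded, but the allocation sentence and the flow chart both contradict it. On either reading the request and the stated allocation need to be reconciled.

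Other objections stand in part:

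- **Missing documents.** Instructions to participants may be in the Recruitment and Retention Plan or on the consent pages. The point is therefore limited to the supplied text.
- **Existing safeguards.** The placebo was chosen for matched expectancy, and expectancy is surveyed across groups. The survey can detect a loss of matching but cannot prevent it. Seeing a neighbour's apps does not by itself reveal which set is the comparator.
- **Size.** The even-spread table favours clustered recruitment, and under wide scatter few participants are affected. This is why both cases are shown.
- **Enforceability.** A request not to compare apps is hard to enforce in communal living and may hint that programs differ. Directors at mixed sites would still handle both. These limit the benefit of the change but are not reasons to leave co-residents out of a request the plan already makes.

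**Conclusion.** The concern holds as a minor point. The plan includes a safeguard against disclosure, but its scope does not match individual randomization.

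How many participants are affected depends on enrollment per site, which the documents do not give. These are co-location figures only. The chance of disclosure, and the size and direction of any bias in the self-reports, are unknown.

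The conclusion assumes that allocation is by individual, as stated, and that the unavailable documents contain no wider instruction. If nearly every site enrolls one person, the point has little effect. Because the primary aim is feasibility, with limited-efficacy testing as the fourth marker of success, it does not threaten the study's main purpose.

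**What to change.** First confirm that allocation is by individual participant, and check the Recruitment and Retention Plan and the consent pages for any wider instruction. If there is none, replace the request in the Protocol section with wording such as:

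> Participants are asked not to discuss or show their assigned apps to other study participants, in their own or other communities, and resident directors are asked not to compare programs between participants, except as needed for technical help.

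Repeat it in the planned webinar for resident directors.

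Optionally, add one neutral item to the planned survey asking whether the participant discussed their program with other participants, and report it by arm. Place it after all outcome scales and interview questions so that it cannot influence them. For a pilot leading to a larger application, knowing how often this happens would be useful in itself.

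The cost is one reworded sentence, a line in the webinar and, if wanted, one survey item. Participants face one slightly broader request, with the small risk of hinting that programs differ.

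### Placebo sessions are prescribed at about 30 minutes against 36 in both training arms, with no reason given, so comparisons with placebo are not matched on training time

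*Combined protocol and SAP*

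**What the plan says.** The Protocol section lists the three arms and then sets the programme at "6 weeks of training (3 days/week), with each training session lasting 36 minutes (not including self-paced breaks". It continues: "Each participant in the DT and nDT groups will engage in 12 3-minute blocks of submodules in each training session". Within that total, "those in the nDT group will play each of the three submodules 4 times equally", while DT participants have their 12 blocks weighted towards the domains in which they scored worst at baseline.

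The Expectancy-Matched Placebo Control section gives PC the same 6-week, 3-day schedule, but "with each training session lasting ~30 minutes where participants will be asked to use each of the submodules for 10 minutes", again leaving out self-paced breaks. It describes the battery as given in the same way as in the other two arms. Two things are offered in support of this control: a survey of 100 naïve individuals showing expectations of benefit equivalent to those for DT, and pilot work with the battery that found "no evidence of improved cognitive control with respect to attention or working memory abilities". The section does not mention the difference in session length.

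On analysis, the Sample size section states: "Significant interactions will be interrogated with appropriate follow-up tests between each group".

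**The concern.** A placebo arm is there to hold everything except the active content equal. The sponsor plainly has this aim: expectancy was tested beforehand and will be surveyed again during the trial (Assessments section). Time on task is another non-specific factor, and matching on expectancy does not cover it.

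With follow-up tests between all groups, two of the three pairwise comparisons (DT versus PC and nDT versus PC) set arms with unequal prescribed time against each other. Any benefit of time on task would tend to favour the training arms, so a positive result against PC would be harder to credit to training content. The pilot is meant to support a later R01 application, so the ambiguity would carry forward. Feasibility is also judged by sessions completed (Mixed Model Approach section). If completion is compared by arm, a shorter PC session makes that comparison less clean too.

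**Working it through.** **Inputs.** From the Protocol section: 12 blocks of 3 minutes per session for DT and nDT; 6 weeks at 3 days a week. From the Expectancy-Matched Placebo Control section: 3 apps at 10 minutes each; 6 weeks at 3 days a week.

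**Step 1: reproduce the stated session lengths** (number of units × minutes per unit).

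- DT and nDT: 12 × 3 = 36 minutes.
- nDT by its own split: 3 submodules × 4 runs × 3 minutes = 36 minutes.
- DT by the plan's worked example: (5 + 5 + 2) × 3 = 36 minutes.
- PC: 3 × 10 = 30 minutes.

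Both stated lengths are reproduced. Both exclude breaks, so breaks do not explain the gap.

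**Step 2: number of sessions.** 6 × 3 = 18 in every arm.

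**Step 3: total prescribed time** (sessions × minutes per session).

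- DT and nDT: 18 × 36 = 648 minutes (10.8 hours).
- PC: 18 × 30 = 540 minutes (9.0 hours).
- Shortfall in PC: 648 − 540 = 108 minutes; 108 / 648 = 16.7%.
- DT versus nDT: 648 − 648 = 0.

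**Step 4: allow for the PC length being approximate.** The range below is an assumption. The shortfall is 18 × (36 − PC length), and its percentage is taken of 648.

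| PC session (min) | PC total (min) | Shortfall (min) | Shortfall (%) |
|---|---|---|---|
| 27 | 486 | 162 | 25.0 |
| 28 | 504 | 144 | 22.2 |
| 30 | 540 | 108 | 16.7 |
| 32 | 576 | 72 | 11.1 |
| 33 | 594 | 54 | 8.3 |

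PC is shorter throughout. The plan also spells out 10 minutes for each of three apps, so the approximation cannot reasonably be stretched to 36.

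**Step 5: check the fix.** 3 × 12 = 36 minutes; 18 × 36 = 648 minutes in every arm; difference 0.

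The effect on cognitive scores cannot be calculated, because the documents contain no figure linking minutes of use to outcome.

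**The case against.** The strongest reply concerns weight, since the facts are not in dispute. This is a feasibility pilot. Its efficacy marker concerns responsiveness to the two versions of the intervention, most naturally DT and nDT, and those are matched. The plan claims matching on expectancy and never on time. Sessions, days and weeks are equal. PC already differs from training in its whole content, and for the time gap to matter, 2 more minutes each of logic games, language learning and Tai Chi would have to raise cognitive control scores. The pilot work argues against that.

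Much of this stands, and it is why the point is modest. It does not remove the point. The PC comparisons are part of the planned analysis. The pilot result covers attention and working memory but does not mention goal management, the third trained domain, and the pilot session length is not given.

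A second reply is that the 36-minute sentence in the Protocol section follows the list of all three arms, so the difference may be a drafting inconsistency and not a choice. That is possible. The specific PC text most likely governs, and on either reading the intended length needs settling.

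A third is that the remedy has its own unknowns. The documents do not say how the 10 minutes per app is controlled, or what session length the expectancy survey and the pilot assumed. This is fair, and it is taken up in the fix.

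**Conclusion.** The concern holds. As written, PC is prescribed 6 minutes less per session and 108 minutes (16.7%) less in total than either training arm, with no reason and no adjustment. This rests on the specific PC text governing that arm and on 18 sessions as prescribed. Under the assumed range of 27 to 33 minutes the shortfall is 8.3% to 25%.

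The consequence is limited to DT versus PC and nDT versus PC. Its direction would tend to favour training; its size is unknown, and the pilot work suggests it is not large. It does not threaten the feasibility aim, but it is avoidable and should be corrected before launch.

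**What to change.** In the Expectancy-Matched Placebo Control section, ask PC participants to use each app for 12 minutes instead of 10, and confirm in the Protocol section that the 36-minute session applies to all three arms.

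The cost is 2 more minutes per app, 6 per session, for the 40 PC participants. No extra participants are needed. If the 10 minutes is set by instruction, as the wording suggests, only the instruction changes; if an app timer enforces it, that setting changes too. Because the session length behind the earlier expectancy survey is not stated, the in-trial expectancy survey should be used to recheck matching at the new length.

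If the shorter session is intended, give the reason, describe PC as expectancy-matched but not time-matched, and report actual minutes of use by arm where the data allow. The Infrastructure Support section already provides the route: "Each app will be configured to wirelessly transmit data automatically to our secure HIPPA-compliant server at UCSF when each training session is completed". This alternative discloses the imbalance but does not remove it, so equalising the time is preferable.
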